the duration of the COVID-19 pandemic, Biopsy Visit 208 should be completed -4 weeks to +6 months of the scheduled time point listed in Appendix 2-C.

- If a participant needs a for-cause biopsy within 8 weeks prior to a scheduled protocol visit, complete all clinical and mechanistic assessments listed in Appendix 5 at the time of the for-cause biopsy.
 - If the scheduled protocol visit occurs during Appendix 1A, complete all clinical assessments noted for the Appendix 1A visit but do not complete any mechanistic collections.
 - If the scheduled protocol visit is listed in Appendices 2-4, the for-cause biopsy visit will take the place of the scheduled protocol visit.
- If the Appendix 4 visit occurs within 1 month (4 weeks) of a scheduled protocol Appendix 2 visit, complete the Appendix 2 visit while collecting all mechanistic samples listed in the Appendix 4 visit in lieu of completing an additional visit.

Table 4. Frequency of Liver Function Tests

Population	Timing	Frequency
For all participants who initiate immunosuppression withdrawal	During immunosuppression withdrawal	Every 3 weeks*
	≤ 26 weeks post immunosuppression withdrawal	Every 4 weeks
	26-52 weeks post immunosuppression withdrawal	Every 8 weeks
	> 52 weeks post immunosuppression withdrawal	Every 12 weeks
	During Rejection	Liver function tests after the rejection episode per standard of care until resolution as determined by the investigator
Additional assessment for participants who successfully complete immunosuppression withdrawal and then restart immunosuppression therapy	26 weeks post immunosuppression restart	Once

*Every 2 weeks between Visits 103-105.

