APPENDIX 2. SCHEDULE OF EVENTS – POST WITHDRAWAL FOLLOW-UP

IMPORTANT NOTE: For the duration of the COVID-19 pandemic, follow the COVID-19 Modified Appendix 2-C instead (per Section 6.2).

IS Withdrawal Follow-up Weeks ¹	0	13	26	52	78	104	130	156
Visit Number ^{2,3}	201 ⁴	202	203	204	205	206	207	208
General Assessments								
Limited physical exam	X	X	X	X	X	X	X	X
Vital signs including weight	X	X	X	X	X	X	X	X
Quality of Life Questionnaires	X		X	X	X	X	X	X
Status Change since prior visit ⁵	X	X	X	X	X	X	X	X
Telephone consultation ⁶	X							X
ECG					Prior to restarting tacrolimus ⁷			
Local Clinical Laboratory Assessments								
LFTs ⁸		Every 4 weeks		Every 8 weeks			Every 12 weeks	
CBC w/differential	X	X	X	X	X	X	X	X
Comprehensive metabolic panel, includes LFTs	X	X	X	X	X	X	X	X
Liver biopsy				X				X
Mechanistic Laboratory Assessments								
Frozen PBMC collection	X		X	X		X		X
Serum collection	X		X	X		X		X
Whole blood collection	X		X	X		X		X
Urine pellet collection	X		X	X		X		X
Fecal collection ⁹	X		X	X		X		X
Liver biopsy collection				X				X

¹ The assessments outlined in Appendix 2 should be completed for all participants who initiated and successfully completed immunosuppression withdrawal. Follow-up should begin within 2 weeks of the date of completion of the participant's last taper level (see section 3.1.3).

² If a for-cause liver biopsy is needed, follow all assessments specified in Appendix 5. If the for-cause biopsy occurs within 8 weeks prior to a scheduled protocol visit, complete all clinical and mechanistic assessments listed in Appendix 5 at the time of the for-cause biopsy. The for-cause biopsy visit will take the place of the scheduled protocol visit.

³ If a participant restarts immunosuppression after successfully completing immunosuppression withdrawal, follow the assessments listed in Appendix 4. **Appendix 2 visits to be completed in addition and concurrently with Appendix 4.**

⁴ For any participant requesting early termination from the study, follow all assessments specified here, Visit 201.

⁵ Includes assessment of change in adverse events and concomitant medications. Changes should be recorded in eCRFs as appropriate.

⁶ Complete following the performance of each liver function test assessment done outside of a transplant center clinical visit; AEs and concomitant medications to be reviewed.

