APPENDIX 3. SCHEDULE OF EVENTS – SAFETY FOLLOW-UP

IMPORTANT NOTE: For the duration of the COVID-19 pandemic, follow the COVID-19 Modified Appendix 3-C instead.

Safety Follow-up Weeks ¹	0	13	26	52	104	156
Visit Number ²	301 ^{3,4}	302	303	304	305	306
General Assessments						
Limited Physical Exam	X	X	X	X	X	X
Vital signed including weight	X	X	X	X	X	X
Quality of Life Questionnaires	X		X	X	X	X
Status Change since prior visit ⁵	X	X	X	X	X	X
Telephone consultation ⁶	X					X
ECG			Prior to restarting tacrolimus if on MMF monotherapy ⁷			
Local Clinical Laboratory Assessments						
LFTs ⁸		Every 4 weeks		Every 8 weeks		Every 12 weeks
CBC w/differential	X	X	X	X	X	X
Comprehensive metabolic panel, includes LFTs	X	X	X	X	X	X
Mechanistic Laboratory Assessments						
Frozen PBMC collection	X		X	X	X	X
Serum collection	X		X	X	X	X
Whole blood collection	X		X	X	X	X
Urine pellet collection	X		X	X	X	X
Fecal collection	X		X	X	X	X

¹ The assessments outlined in Appendix 3 should be completed for all participants who initiated but did not complete immunosuppression withdrawal. Follow-up should begin within 2 weeks of the date of immunosuppression withdrawal failure (see section 3.1.3.5).

² If a for-cause liver biopsy is needed, follow all assessments specified in Appendix 5. If the for-cause biopsy occurs within 8 weeks prior to a scheduled protocol visit, complete all clinical and mechanistic assessments listed in Appendix 5 at the time of the for-cause biopsy. The for-cause biopsy visit will take the place of the scheduled protocol visit.

³ If a for-cause liver biopsy visit took place within 8 weeks of visit 301, all mechanistic assessments listed in Appendix 5 at the time of the for-cause biopsy visit should be completed in lieu of mechanistic assessments listed for visit 301.

⁴ For any participant requesting early termination from the study, follow all assessments specified here, Visit 301.

⁵ Includes assessment of change in adverse events and concomitant medications. Changes should be recorded in eCRFs as appropriate.

⁶ Complete following the performance of each liver function test assessment done outside of a transplant center clinical visit; AEs and concomitant medications to be reviewed.

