APPENDIX 5. SCHEDULE OF EVENTS – FOR-CAUSE BIOPSY

IMPORTANT NOTE: For the duration of the COVID-19 pandemic, follow the COVID-19 Modified Appendix 5-C instead.

Visit Number	FCB ¹	PBV ²
General Assessments		
Limited physical exam	X ³	X
Vital signs including weight	X	X
Status Change since prior visit ⁴	X	X
ECG	Prior to restarting tacrolimus ⁵	
Local Clinical Laboratory Assessments		
CBC w/differential	X	X
Comprehensive metabolic panel, includes LFTs	X	X
Liver biopsy	X	
Mechanistic Laboratory Assessments		
Frozen PBMC collection	X	
Serum collection	X	
Whole blood collection	X	
Urine pellet collection	X	
Fecal collection	X	
Liver biopsy collection	X	

² Participants in post withdrawal follow-up (Appendix 2) or safety follow-up (Appendix 3) who experience a rejection episode will have transplant center visits every 13 weeks until liver function test normalization. If post rejection visits are needed outside of the scheduled Appendix 2 or Appendix 3 visits, follow all assessments specified here, Visit PBV, for those visits.

³ Complete only if for-cause biopsy visit occurs within 8 weeks prior to a scheduled protocol visit and replaces that scheduled visit.

⁴ Includes assessment of change in adverse events and concomitant medications. Changes should be recorded in eCRFs as appropriate.

⁵ For participants who completed CNI withdrawal and need to restart tacrolimus for biopsy confirmed or presumed acute rejection, complete the ECG assessment (also noted in Appendix 2 & Appendix 3) prior to restarting tacrolimus (section 6.8). A follow-up ECG will be performed within 7 days after tacrolimus has been restarted. ECG findings will be monitored per the site's standard of care until the subject is taking a stable dose of tacrolimus. Evidence of a prolonged QTc interval will be appropriately evaluated and treated.

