Changes in renal function (defined as estimated GFR calculated by CKD-EPI) in tolerant versus non-tolerant participants at 1, 2 and 3 years after completing immunosuppression withdrawal for tolerant subjects and failure of withdrawal for non-tolerant subjects.	
Baseline eGFR will be calculated from data collected at Visit 0. If Visit 0 data is missing, Visit -1 data will be used. Data collected closest to 1-year post completion/failure, within +/- 2 months, will be used to calculate eGFR at 1. The same process will be followed for 2 and 3-years after completion/failure.
 
eGFR will be calculated using the CKD-EPI equation:
 $\text{GFR} = 141 * \min(\text{Scr}/\kappa, 1)^\alpha * \max(\text{Scr}/\kappa, 1)^{-1.209} * 0.993^{\text{Age}} * 1.018 \text{ [if female]} * 1.159 \text{ [if black]}$ 
Scr: serum creatinine (mg/dL) κ: 0.7 for females and 0.9 for males α: -0.329 for females and -0.411 for males
 
Change in eGFR will be calculated as: 1-year post completion/failure eGFR – baseline eGFR
 
Thus positive value will indicate increase kidney function.
 
Changes will be summarized descriptively by tolerance status.
	ITT, PP
Changes in Quality of Life in tolerant versus non-tolerant participants and in all participants at baseline versus the end of study participation, as measured by the NIDDK Liver Transplantation Database Quality of Life Form.	The questionnaire filled out at Visit 0 will serve as the baseline questionnaire. The questionnaire filled out closest to the end of study participation will serve as the end of study questionnaire. For subjects	ITT, PP

	
with complete follow-up, this will be the questionnaire completed at Visit 208 or Visit 306.
 
The questionnaire will be summarized into five domains as outlined by Bell et al. The domains include measures of disease, psychological status, personal function, social and role function, and general health perception.
 
The change in each domain will be calculated as: Domain Score at End of Study – Domain score at Baseline.
 
The baseline, end of study, and change from baseline domain scores will be summarized descriptively by tolerance status.
 
If the data permits, a spaghetti plot visualizing each component score over time will be produced. Each graph will have two panels—one depicting the tolerant subjects, the other depicting the non-tolerant subjects.
	

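### A for-cause biopsy visit can replace a follow-up visit that carries quality-of-life forms, but Appendix 5 lists none, so a few forms, occasionally the final one, are lost around suspected rejection

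*Protocol*

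**What the plan says.** **The replacement rule.** Protocol 6.1.1 covers a participant who "needs a for-cause biopsy within 8 weeks prior to a scheduled protocol visit". For follow-up visits, "If the scheduled protocol visit is listed in Appendices 2-4, the for-cause biopsy visit will take the place of the scheduled protocol visit". Footnote 2 of Appendix 2 repeats this ("The for-cause biopsy visit will take the place of the scheduled protocol visit"), as do footnote 2 of Appendix 3 and footnote 3 of Appendix 4. Visits during withdrawal are treated differently: there, sites "complete all clinical assessments noted for the Appendix 1A visit but do not complete any mechanistic collections".

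**The biopsy visit.** Appendix 5 has no quality-of-life row. Its footnote 3, on the limited physical exam, reads "Complete only if for-cause biopsy visit occurs within 8 weeks prior to a scheduled protocol visit and replaces that scheduled visit".

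**Visit 301.** Footnote 3 of Appendix 3 says that, when a for-cause biopsy took place within 8 weeks of Visit 301, the biopsy visit's mechanistic assessments "should be completed in lieu of mechanistic assessments listed for visit 301". It does not mention the clinical items or questionnaires.

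**The analysis.** For both instruments SAP Table 7-2 takes Visit 0 as baseline and, for the end value, states: "The questionnaire filled out closest to the end of study participation will serve as the end of study questionnaire". With complete follow-up this is the Visit 208 or 306 form. The mock table in the SAP appendix defines change as last available minus baseline. Other forms feed a plot over time if the data allow. SAP section 3 rules out imputation unless stated.

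**The concern.** A for-cause biopsy follows unexplained allograft dysfunction (Protocol 6.6.1 and 6.10.1). Whether a form is lost therefore depends on suspected rejection, which is closely tied to the tolerant versus non-tolerant split used to summarise quality of life. The loss comes from the schedule rather than from the participant.

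Footnote 3 of Appendix 5 shows that the authors considered the case of a replaced visit and restored one clinical item for it, but not the questionnaires. Nothing explains why withdrawal visits keep all their clinical assessments and follow-up visits do not.

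The SAP does not guard against the consequence. It gives the end-of-study form no time window, although eGFR in the same table has one of plus or minus 2 months. If the last visit is replaced, a much older form becomes the end value without being flagged.

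**Working it through.** The plan states no figure for this point. The check sets the schedules side by side and counts weeks.

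**1. Is the rule operative?** SAP 7.2.1 accepts a primary-endpoint biopsy from week 44 because of it: 52 − 8 = 44. The SAP relies on the same rule.

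**2. Where the questionnaires fall.**

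| Schedule | Weeks with quality-of-life forms |
|---|---|
| Appendix 2 | 0, 26, 52, 78, 104, 130, 156 |
| Appendix 3 | 0, 26, 52, 104, 156 |
| Appendix 4 (RIS visit) | none |
| Appendix 5 (both columns) | none listed |

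The Visit 0 baseline lies in Appendix 1A and is not exposed to the rule.

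**3. Share of follow-up in which a biopsy displaces a form.** Leaving Visits 201 and 301 aside, the 8-week windows do not overlap:

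- Any form, Appendix 2: 6 × 8 / 156 = 48/156 = 30.8%
- Any form, Appendix 3: 4 × 8 / 156 = 32/156 = 20.5%
- Final form (Visit 208 or 306): 8/156 = 5.1%

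**4. Which share matters for the planned estimate?** The change score uses only Visit 0 and the last form, so the 5.1% window is the relevant one. An intermediate form matters to the score only if the participant leaves the study without completing a later one.

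**5. Age of the substitute when the final form is displaced.**

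- Appendix 2: 156 − 130 = 26 weeks
- Appendix 3: 156 − 104 = 52 weeks

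The displacing biopsy falls in weeks 148 to 156. The substitute form therefore precedes it by at least 148 − 130 = 18 weeks or 148 − 104 = 44 weeks, and may predate the episode altogether.

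**6. Illustration in numbers of forms.** The documents give neither the count nor the timing of for-cause biopsies. Assume that 24 to 42 participants (40% to 70% of 60) each have one, spread evenly over the 156 weeks:

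| Participants with a biopsy | Any form, all on Appendix 2 | Any form, all on Appendix 3 | Final form |
|---|---|---|---|
| 24 | 7.4 | 4.9 | 1.2 |
| 42 | 12.9 | 8.6 | 2.2 |

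That is about 5 to 13 forms at any visit, but only 1 to 2 end-of-study forms.

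**7. Visit 301.** It is due within 2 weeks of withdrawal failure (Protocol 6.1.1), so a biopsy that establishes failure will often fall inside its 8-week window. Footnote 2 of Appendix 3 would replace the whole visit; footnote 3 replaces only its mechanistic part. Sites could act on either.

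**The case against.** **The appendix may be incomplete as read.** The FCB column of Appendix 5 carries a footnote 1 that does not appear in the available text. It could address replaced visits. The absence of a questionnaire row is therefore likely rather than certain, and the sponsor can settle it at once.

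**Little of the planned analysis is exposed.** Quality of life is a descriptive secondary endpoint, and intermediate forms enter no planned estimate. This stands. A reader might infer from the 31% and 21% windows that a comparable share of the endpoint is at risk. The documents do not support that: those windows govern mainly the plots. Even timing is also an assumption. Biopsies whose next visit is a withdrawal visit cost no form.

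**The direction of bias is unknown.** A reader might infer that the non-tolerant group loses its worst scores. The documents report no quality-of-life data around rejection. Biopsies are triggered by laboratory dysfunction, and Protocol 3.4 describes most rejection episodes as mild. Loss follows suspected rejection, so a tolerant participant with a negative biopsy loses a form too.

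**Visit 301 may be protected.** Footnote 3 can be read as a specific provision qualifying footnote 2, which would keep the questionnaires. It is thus wrong to say that Visit 301 forms are lost; the two footnotes simply disagree.

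**The COVID-19 schedules collect the forms by mail.** Appendices 2-C and 3-C do so, and their biopsy footnotes omit the replacement sentence. This limits the problem while those schedules apply.

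**Conclusion.** The gap holds on the text available. A for-cause biopsy visit can displace a visit that carries SF-36 and NIDDK forms, and the schedule that takes over lists neither. The loss is selective around suspected rejection.

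Its effect on the planned change score is small: mainly an 8-of-156-week window (5.1%), or about 1 to 2 final forms under the illustration's assumptions on count and timing. Where it occurs, the end value is normally 26 or 52 weeks out of date. No direction of bias can be claimed. The conclusion assumes that the missing footnote 1 of Appendix 5 does not already require the forms.

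A reader might also infer that the SAP needs a repeated-measures mixed model. It does not: the protocol defines a baseline-to-end comparison, and a fixed-week model would change that endpoint. Such a model is optional. The point is worth acting on because the repair is cheap.

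**What to change.** 1. **Appendix 5:** add the SF-36 and NIDDK questionnaires to the FCB column, on site or by mail, whenever that visit replaces one that carries them. The condition can follow the wording of footnote 3.
2. **Appendix 3:** reconcile footnotes 2 and 3 so that the Visit 301 questionnaires are clearly kept.
3. **SAP Table 7-2:** set a time window for the end-of-study form, and report by tolerance group when that form was completed and how many forms fell outside the window.

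**Cost:** two questionnaires for the few participants affected, one conditional row and a footnote edit in the protocol, and a few lines in the SAP. If collection can no longer be changed, item 3 can still be done and would show how far the loss reached the analysis.

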6.2 COVID-19 PANDEMIC SCHEDULE OF EVENTS

During the pandemic, participants should follow the COVID-19 schedule of events (Appendices 2-C, 3-C, and 5-C) to prioritize critical safety follow-up visits and assessments following completion or discontinuation of immunosuppression withdrawal. Site investigators should ensure that all research activities are conducted in accordance with state, local, and institutional guidance. Each institution will

ensure that standard COVID-19 screening and precautions are in place before any on-site study visits or when participants resume the regular schedule of events.

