APPENDIX 1A. SCHEDULE OF EVENTS – IMMUNOSUPPRESSION WITHDRAWAL

	CNI Withdrawal										MMF Withdrawal (if applicable)		
	Prednisone Withdrawal (if applicable)												
Taper Level	N/A	0	1	2	3	4	5	6	7	8	0	1	2
Visit Number ^{1,2}	-1	0	101 ³	102	103	104	105	106	107	108 ⁴	109 ⁵	110 ⁶	111
General Assessments													
Informed consent for ISW	X												
Medical and demographic history including liver transplant specifics	X												
Complete physical exam including height	X												
Vital signs including weight	X	X			X		X				X		
Limited physical exam		X			X		X				X		
Quality of Life Questionnaires		X									X		
Status Change since prior visit ⁷	X									X	X		X
Telephone consultation			X	X		X		X	X	X		X	X
Banked donor sample availability ⁸	X												
ECG		X ⁹											
Local Clinical Laboratory Assessments													
LFTs	X	Every 3 weeks			Every 2 weeks		Every 3 weeks			Every 3 weeks			
CBC w/differential	X	X			X		X				X		
Comprehensive metabolic panel, includes LFTs	X	X			X		X				X		
Urine or blood hCG	X												
Autoantibody panel ¹⁰	X												
Viral Serology/Antibody/Immunoassay tests ^{11,12}	X												

¹ Up to 3 nonconsecutive pauses may occur during visits 101-111 (if needed) as outlined in section 3.1.3.4.

² If a for-cause liver biopsy is needed, follow all assessments specified on Appendix 5. If the for-cause liver biopsy occurs within 8 weeks of a scheduled visit, complete all clinical and mechanistic assessments listed in Appendix 5 at the time of the for-cause liver biopsy. Complete all clinical assessments during the scheduled visit but do not complete any mechanistic collections.

³ CNI withdrawal must begin within 7 days of Visit 0 and after demonstrating stable liver function (see section 3.1.3.1).

⁴ Move to visit 109 if the participant is on a mycophenolate compound therapy or to visit 201 (Appendix 2) if the participant was on CNI alone or CNI and prednisone and successfully completed withdrawal. Move to visit 301 (Appendix 3) if the participant failed to successfully withdraw from immunosuppressive treatment.

⁵ Complete within 2 weeks of the date of completion of the participant's last CNI taper level (see section 3.1.3) if the participant is on a mycophenolate compound therapy.

⁶ Mycophenolate compound immunosuppression withdrawal to be initiated once the participant has completed CNI withdrawal and upon confirmation of at least 3 weeks of stable liver function (see section 3.1.3.3).

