APPENDIX 2-C. (COVID-19 MODIFIED) SCHEDULE OF EVENTS – POST WITHDRAWAL FOLLOW-UP

IS Withdrawal Follow-up Weeks ¹	0	13	26	52	78	104	130	156
Visit Number ²	201 ³	202	203	204	205	206	207	208
General Assessments								
Limited physical exam								X
Vital signs including weight								X
Quality of Life Questionnaires ⁴				X	X	X	X	X
Status Change since prior visit								X
Telephone consultation ⁵	X							X
ECG				Prior to restarting tacrolimus ⁶				
Local Clinical Laboratory Assessments								
LFTs ⁷				Every 8 weeks		Every 12 weeks		
CBC w/differential			X	X	X	X	X	X
Comprehensive metabolic panel, includes LFTs			X	X	X	X	X	X
Liver biopsy								X
Mechanistic Laboratory Assessments								
Frozen PBMC collection								X
Serum collection								X
Whole blood collection								X
Urine pellet collection								X
Fecal collection								X
Liver biopsy collection								X

¹ The assessments outlined in Appendix 2 should be completed for all participants who initiated and successfully completed immunosuppression withdrawal. Follow-up should begin within 2 weeks of the date of completion of the participant's last taper level (see section 3.1.3).

² If a for-cause liver biopsy is needed, follow Appendix 5.

³ For any participant requesting early termination from the study, collect the following assessments if possible: telephone consultation with AE and concomitant medication update, CBC with diff, and comprehensive metabolic panel including LFTs.

⁴ Complete Quality of Life assessment by mail.

⁵ Complete following the performance of each liver function test assessment done outside of a transplant center clinical visit; AEs and concomitant medications to be reviewed.

⁶ For participants who need to restart tacrolimus for biopsy-confirmed or presumed acute rejection (see section 6.8). A follow-up ECG will be performed within 7 days after tacrolimus has been restarted. ECG findings will be monitored per the site's standard of care until the participant is taking a stable dose of tacrolimus. Evidence of a prolonged QTc interval will be appropriately evaluated and treated.

⁷ If participant experiences a rejection episode, complete liver function tests per standard of care until resolution as determined by the investigator. Record all liver function tests performed during a rejection episode in EDC.

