APPENDIX 3-C. (COVID-19 MODIFIED) SCHEDULE OF EVENTS – SAFETY FOLLOW-UP

Safety Follow-up Weeks ¹	0	13	26	52	104	156
Visit Number ²	301 ³	302	303	304	305	306
General Assessments						
Quality of Life Questionnaires ⁴					X	X
Telephone consultation ⁵	X-----					X
ECG			Prior to restarting tacrolimus if on MMF monotherapy ^{6,7}			
Local Clinical Laboratory Assessments						
LFTs ⁸					Every 12 weeks	
CBC w/differential					X	X
Comprehensive metabolic panel, includes LFTs					X	X

¹ The assessments outlined in Appendix 3 should be completed for all participants who initiated but did not complete immunosuppression withdrawal. Follow-up should begin within 2 weeks of the date of immunosuppression withdrawal failure (see section 3.1.3.5).

² If a for-cause liver biopsy is needed, follow Appendix 5.

³ For any participant requesting early termination from the study, collect the following assessments if possible: telephone consultation with AE and concomitant medication update, CBC with diff, and comprehensive metabolic panel including LFTs.

⁴ Complete Quality of Life assessment by mail.

⁵ Complete following the performance of each liver function test assessment done outside of a transplant center clinical visit; AEs and concomitant medications to be reviewed.

⁶ Perform locally or at study site, as necessary.

⁷ For participants on MMF monotherapy who need to restart tacrolimus for biopsy-confirmed rejection or presumed acute rejection (see section 6.8). A follow-up ECG will be performed within 7 days after tacrolimus has been restarted. ECG findings will be monitored per the site's standard of care until the subject is taking a stable dose of tacrolimus. Evidence of a prolonged QTc interval will be appropriately evaluated and treated.

⁸ If participant experiences a rejection episode, complete liver function tests per standard of care until resolution as determined by the investigator. Record all liver function tests performed during a rejection episode in EDC.

APPENDIX 4. SCHEDULE OF EVENTS—ADDITIONAL, CONCURRENT FOLLOW-UP FOR PARTICIPANTS WHO RESTART IMMUNOSUPPRESSION AFTER SUCCESSFUL COMPLETION OF IMMUNOSUPPRESSION WITHDRAWAL - THESE VISITS ARE TO OCCUR CONCURRENTLY WITH THE VISITS OUTLINED IN APPENDIX 2

IMPORTANT NOTE: For the duration of the COVID-19 pandemic, do not follow this Appendix.

Additional Follow-Up Weeks ¹	26
Visit Number ^{2,3}	RIS ⁴
General Assessments	
Limited physical exam	X
Vital signs including weight	X

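### The pandemic schedule that governs follow-up after completed withdrawal (Appendix 2-C) prints no routine liver test before week 26, where the unreconciled Table 4 requires about 6

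*Protocol*

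**What the plan says.** Table 4 (protocol Section 6.1.1) sets LFT frequency "For all participants who initiate immunosuppression withdrawal". After withdrawal it asks for a test every 4 weeks to week 26, every 8 weeks to week 52, and every 12 weeks from then on. The ordinary Appendices 2 and 3 print the same three intervals. Table 4 has no pandemic exception, although nearby text in Section 6.1.1 does: Visit RIS6 is cancelled and the Visit 208 biopsy window is widened.

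Section 6.1.1 opens by sending the reader to Section 6.2 for the schedules to use in the pandemic. Section 6.2 says: "During the pandemic, participants should follow the COVID-19 schedule of events (Appendices 2-C, 3-C, and 5-C) to prioritize critical safety follow-up visits and assessments". The note on Appendix 2 tells sites to "follow the COVID-19 Modified Appendix 2-C instead (per Section 6.2"), and the note on Appendix 3 reads "For the duration of the COVID-19 pandemic, follow the COVID-19 Modified Appendix 3-C instead".

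Appendix 2-C has 8-weekly and 12-weekly LFT entries but no 4-weekly one. Its metabolic panel, which includes LFTs, is marked from week 26 to week 156 only. Appendix 3-C has a single 12-weekly LFT entry and panels at weeks 104 and 156. Footnote 1 of each applies it to everyone in that follow-up group.

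**The concern.** Sites are directed to a schedule that omits the closest liver monitoring after withdrawal, while the table requiring that monitoring stands unamended. A site following 2-C as printed would run no routine ALT or GGT in the first 26 weeks after a participant stops all immunosuppression.

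The protocol's own safety case relies on that period. Section 1.4.1.1 says the trial is designed to detect rejection early, including soon after immunosuppression stops. Section 1.4.1.2 treats close liver monitoring during and after withdrawal as essential, and Section 3.4 links frequent testing to preventing irreversible damage. Under Section 6.6.1, ALT and GGT define allograft dysfunction, and dysfunction that persists without another explanation leads to the for-cause biopsy. Without the routine test, clinically silent dysfunction has no scheduled route to a biopsy.

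Rejection after completed withdrawal is a real possibility. In one arm of the earlier trial described in Section 1.3.1, 4 of 9 participants who completed withdrawal later resumed immunosuppression for rejection (timing not given).

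**Working it through.** The check is a count of scheduled tests; no power or precision figure is involved.

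**Table 4 requirement**
- To week 26, every 4 weeks: weeks 4, 8, 12, 16, 20, 24 = 6 tests.
- Weeks 26 to 52, every 8 weeks: weeks 34, 42, 50 = 3 tests. Counting from week 24 gives weeks 32, 40, 48, also 3.
- Total through week 52: 6 + 3 = 9.

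**Appendix 2-C before week 26**
- The 8-weekly entry sits in the week-52 column and the first panel at week 26, so 0 tests are printed.
- Counted strictly, the shortfall is 6 − 0 = 6.
- Section 6.1.1 allows ±2 weeks for centre visits. A week-26 panel drawn at week 24 (26 − 2) covers the week-24 test, leaving weeks 4, 8, 12, 16 and 20, a shortfall of 5.
- The first printed test moves from week 4 to week 26, which is 26 − 4 = 22 weeks later.
- Sensitivity: if the 8-weekly cell were stretched back to week 0, tests would fall at weeks 8, 16 and 24, leaving 6 − 3 = 3 short. The panel row, blank before week 26, argues against that reading. The 4-weekly entry is missing wherever the cells sit.

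**Appendix 3-C through week 52**

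| Where the 12-weekly entry starts | Tests printed | Shortfall against 9 |
|---|---|---|
| After week 52 (as placed, week-104 column) | 0 | 9 |
| Week 26 | weeks 38, 50 = 2 | 7 |
| Week 0 | weeks 12, 24, 36, 48 = 4 | 5 |

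Cell positions in this table were flattened when the text was extracted, hence the range. Under every reading the 4-weekly and 8-weekly entries are absent.

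The panels that 3-C omits at weeks 13, 26 and 52 fall within 1 to 2 weeks of Table 4 tests (13 against 12, 26 against 24, 52 against 50), so they are not added to the shortfall.

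**Evidence that Table 4 was not reconciled**
- Its last row still asks for a test 26 weeks after immunosuppression is restarted, although the visit at that time is cancelled for the pandemic.
- Section 6.1.1 keeps a ±5-day window for local laboratory work in the first 26 weeks after withdrawal.
- The telephone rows of 2-C and 3-C still begin at week 0. Their footnote reads "Complete following the performance of each liver function test assessment done outside of a transplant center clinical visit", which presupposes such tests.

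**The case against.** A reader might infer that a site cannot tell which schedule governs. The documents do not support that: Sections 6.1.1 and 6.2 and the notes on Appendices 2 and 3 all point to the pandemic schedules. But this order of precedence does not remove the problem, because the schedule it selects is the one without the tests. If Table 4 was nonetheless meant to bind, the 2-C row is wrong.

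The strongest objection is that the early columns are blank because nobody was left in them. The signs are good:
- There is no pandemic version of Appendix 1A.
- 2-C omits the week-52 biopsy, which the primary endpoint needs, and only Visit 208 gets a pandemic window.
- Mailed quality-of-life forms, which need no visit, are blank early on too.

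This is plausible, and it counts against a second inference a reader might draw: that the sponsor chose to stop testing newly weaned participants, or that some went untested. Nothing in the documents shows either.

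Still, the explanation is nowhere stated. 2-C prints a week-26 panel and 8-weekly tests, so an empty cohort before week 26 is not shown. Appendix 1A footnote 4 still routes participants "to visit 201 (Appendix 2) if the participant was on CNI alone or CNI and prednisone and successfully completed withdrawal", and adds: "Move to visit 301 (Appendix 3) if the participant failed to successfully withdraw from immunosuppressive treatment". Those are the week-0 columns of the two schedules. This is standing text, as is footnote 1 of 2-C and 3-C, which still names Appendices 2 and 3. It shows an open route, not that anyone took it.

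Some safeguards remain: telephone review, for-cause biopsy under Appendix 5-C, and the rule "If participant experiences a rejection episode, complete liver function tests per standard of care until resolution as determined by the investigator". These help once a problem is suspected. They do not replace routine tests for finding silent dysfunction.

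**Conclusion.** The point holds, chiefly for Appendix 2-C. The governing pandemic schedule prints no routine liver test before week 26 after completed withdrawal, against about 6 in Table 4, leaving 5 to 6 without a counterpart. This rests on the column placement described above, which the panel row supports.

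The 3-C gap (5 to 9 tests through week 52) matters less. Most of those participants are back on immunosuppression after rejection, with standard-of-care LFTs until resolution, or were held at their current dose when a pause ran out (Section 3.1.3.4). Its count also depends on cell position.

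The number of participants exposed is not given and may be zero, so the harm is potential. No effect on the primary endpoint or any planned estimate is shown. The correction is still worth making, because a printed rule is wrong whichever document was meant to prevail and the monitoring concerned is one the protocol calls essential.

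**What to change.** State in Section 6.2 that the Table 4 LFT frequencies continue during the pandemic through local laboratories. Restore the 4-weekly entry to week 26 in the LFT row of 2-C. In 3-C, add the 4-weekly entry to week 26 and the 8-weekly entry from week 26 to week 52.

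If the sponsor can confirm that no participant is or will be in those weeks, two header lines would do instead: 2-C applies only from week 26, and 3-C only after week 52.

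The cost is one sentence and two table rows, or two header lines. No test is added beyond Table 4, and Section 6.4.1 already permits local laboratories to perform them.
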